## V. DESIGN

This is a randomized, placebo-controlled, cross-over, single-center trial. Study drug is Botulinum toxin type A (BOTOX®). Subjects who meet the inclusion criteria for the study will be randomized to either the treatment or placebo arm.

**ARM 1 - Treatment:** Injection solution will consist of 100 units of BOTOX® in 10 cc of preservative free normal saline, or

**ARM 2 - Placebo:** Injection solution will consist of 10 cc preservative free normal saline.

The Week 16 Visit will be the end of the study participation for those subjects in Arm 1 and who did not develop ED (as defined as a drop in IIEF scores of more than 4 points from Baseline IIEF score). The Week 16 Visit will be the end of study participation for subjects in Arm 2 and who developed ED. For subjects in Arm 2, crossover to BOTOX treatment will begin after the Week 16 Visit by repeating the study schedule as for Week 0 to Week 16. Continuation visits at Months 6, 9, and 12 will occur for subjects in Arm 1 and who developed ED.

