## I. BACKGROUND AND RATIONALE

Over the past several years botulinum toxin type A (BTX-A, BOTOX®) has been used in many applications to prevent scar formation. Gassner and Sherris previously found that chemoimmobilization of facial wounds with BTX-A improved wound healing and cosmetic appearance. These clinical findings are supported by a randomized, double-blinded, placebo-controlled study showing a significant improvement in scar appearance in BTX-A treated facial wounds compared to saline injected controls. In addition, we recently published the first article demonstrating that BTX-A is effective in treating urethral strictures, which are caused by scar formation. Finally, Comperat and colleagues demonstrated that BTX-A injections in the bladder leads to less fibrosis. In the study, bladder wall specimens were obtained from cystectomy in 45 patients with neurogenic overactive bladders with and without injection of botulinum toxin A into the detrusor. Bladder wall specimens were evaluated for inflammation, edema, and fibrosis. When comparing specimen from patients who had received botulinum toxin injection to those from patients who had not, there was no difference concerning inflammation and edema. However, patients who had received botulinum toxin injection showed significantly less fibrosis of the bladder wall than those who had not received the toxin injection ( $p < 0.00073$ ).

A major contributor to fibrosis and scar formation is thought to be tension from the underlying muscle contractions acting on the wound edges during healing. BTX-A acts at the neuromuscular junction by blocking vesicle transport of acetylcholine, in essence producing a chemical denervation. By decreasing underlying muscle tension/spasm in healing wounds BTX-A may be a viable option to prevent fibrosis and scar formation.

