## **III. DRUG INFORMATION**

BOTOX® is the brand name for Botulinum toxin type A. For this study's treatment injections, we will be using 100 units of BOTOX® in 10 cc of preservative free normal saline, or 10 cc of preservative free normal saline for placebo.

BOTOX® and Placebo will be provided by Allergan, Inc.

BOTOX® is a purified neurotoxin complex supplied as a sterile, vacuum dried purified botulinum toxin type A, produced from fermentation of Clostridium botulinum type A.

One unit of BOTOX® corresponds to the calculated median intraperitoneal lethal dose (LD 50) in mice. The specific activity of BOTOX® is approximately 20 units/nanogram of neurotoxin protein complex.

BOTOX® blocks neuromuscular transmission by binding to acceptor sites on motor or sympathetic nerve terminals, entering the nerve terminals, and inhibiting the release of acetylcholine. This inhibition occurs as the neurotoxin cleaves SNAP-25, a protein integral to the successful docking and release of acetylcholine from vesicles situated within nerve endings. When injected intramuscularly at therapeutic doses, BOTOX® produces partial chemical denervation of the muscle resulting in a localized reduction in muscle activity. In addition, the muscle may atrophy, axonal sprouting may occur, and extra-junctional acetylcholine receptors

may develop. There is evidence that reinnervation of the muscle may occur, thus slowly reversing muscle denervation produced by BOTOX®.

BOTOX® is not expected to be present in the peripheral blood at measurable levels following IM or intradermal injection at the recommended doses. The recommended doses of neurotoxin administered at each treatment session are not expected to result in systemic, overt distant clinical effects, i.e., muscle weakness, in patients without other neuromuscular dysfunction. However, some clinical systemic effects have been shown by a single fiber electromyography after IM doses of botulinum toxins appropriate to produce clinically observable local muscle weakness.

BOTOX® is contraindicated in the presence of infection at the proposed injection site(s), and in individuals with known hypersensitivity to any ingredient in the formulation.

BOTOX® is supplied in a single-use vial. Each vial contains 100 units of vacuum-dried Clostridium botulinum type A neurotoxin components.

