## VI. RANDOMIZATION PROCEDURES:

The subjects will be randomized to the arms as they are enrolled and meet eligibility criteria. The odd number (1, 3, 5...) of subjects will be in ARM 1 and even numbers (2, 4, 6...) of subjects will be in the ARM 2. The randomization scheme will not result in selection bias.

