## VIII. PROCEDURES

Subjects who meet the inclusion criteria for the study will be randomized to either the treatment or placebo arm. Prior to treatment, all subjects will have a penile injection with Caverject 20mcg/cc to induce a penile erection. During the erect state, penile curvature will be assessed, pictures will be taken for later measurement of penile curvature, and ultrasound will be used to assess penile blood flow and plaque size. A penile duplex with intercavernosal injections of a vasoactive substance is part of our standard care for Peyronies disease diagnosis. Subjects will also be asked to complete the International Index of Erectile Function (IIEF) questionnaire.

Injections will be performed using our standard protocol currently used for verapamil injections, but instead we will be using 100 units of BTX-A in 10cc of preservative free normal saline, or 10cc of preservative free normal saline for placebo and plaque breakdown injections. The standard injection procedure consists of the following:

1. Subjects will be explained the risks and benefits of the procedure and will give informed consent.
2. Blood pressure, pulse, and oxygen saturation will be monitored throughout the procedure.
3. A penile block with 10cc of lidocaine without epinephrine will be given, followed by an observation period of 10 minutes to assure no immediate adverse reaction to lidocaine.
4. Approximately 20 to 30 injections with a 20 gage needle will be given directly into the penile plaque. The skin will not be punctured with each injection, but the needle will move within the plaque. Injection solution will consist of 100 units of BTX-A in 10 cc of preservative free normal saline, or 10 cc of preservative free normal saline.
5. Subjects in the placebo arm will only receive 10 cc of preservative free normal saline.
6. Subjects will be monitored for 1 hour after the procedure to ensure that their vital signs are stable and that there are no signs of penile hematoma.
7. Safety will be assessed by following the subject closely for one hour after the procedure.
8. Subjects will be given strict instructions to call and return to the clinic or the ER for any adverse side effects.

Subjects randomized to ARM 1 will receive one injection of 10 cc preservative normal saline at study start (week 0), followed by 100 U Botox in 10cc saline at visit two (week 4), then saline injections at weeks 8 and 12, thus a total of 4 injections (1 saline, 1 Botox, 2 saline).

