## **XVIII. CONFIDENTIALITY**

Each subject will be assigned a unique, consecutive three-digit identification number (i.e., 001, 002, ...). The study number will be utilized for identification of the subject throughout the study. The clinical study coordinator of the trial will maintain the code that links the name of the participant to their study ID number. The study coordinator will maintain the code in a secured cabinet and the code will be kept confidential. Only the clinical study coordinator and PI can access and view the codes.

The research records will be maintained in the Scott Department of Urology. The computers used for this study are password protected. The data will be kept by the clinical coordinator in a secure locked area. Areas are protected after hours by an electronic door locking systems. The Scott Department of Urology adheres to the HIPAA guidelines.

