## 10. HELPFUL HINTS

- 10.1 Copy the source documentation for the data reported as you abstract the data from the patient's primary record. This could possibly prevent a discrepancy for not being able to document the data reported when reviewed by auditors.
- 10.2 Approximately four weeks prior to the audit, you will receive the list of cases to be audited.
- 10.3 Thoroughly review the protocol for the eligibility criteria, study parameters, treatment requirements and response definitions.
- 10.4 For investigational drug accountability audit, notify the pharmacist, or the person responsible for the drug logs. Be sure the shipping receipts, return forms, transfer forms and drug logs will be available for the audit. Prepare for a tour of the area where the drugs are stored.
- 10.5 Notify the IRB Chairperson that you need documentation of initial and annual approval along with protocol modification approvals for each protocol on the list of cases. This documentation may be in the form of IRB letters of approval from the IRB Chairperson and/or minutes of the IRB meetings.
- 10.6 Once the source documentation is available, compare the data sheets with the medical records for accuracy, paying close attention to dates.
- 10.7 Clearly identify the data in the medical records to facilitate quick retrieval during the audit. It is suggested using colored tabs indicating treatment cycles, dates or week numbers. Be creative - the important point is for you to quickly find the documentation as requested by the auditors.
- 10.8 Be available all day to assist the auditors.
- 10.9 If the original medical records are not available, legible copies may be used.

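### Nothing in the available text masks the subject, injector or image reader, and the odd/even allocation with consecutive IDs works against masking, so curvature and IIEF are open to performance and assessment bias

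*Combined protocol and SAP*

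**What the plan says.** Section V gives the design as "This is a randomized, placebo-controlled, cross-over, single-center trial". Blinding is not among the features. The only mention of it is in Section I, about a cited external study: "These clinical findings are supported by a randomized, double-blinded, placebo-controlled study".

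Section VI allocates by alternation: "The odd number (1, 3, 5...) of subjects will be in ARM 1 and even numbers (2, 4, 6...) of subjects" in Arm 2. Section XVIII adds: "Each subject will be assigned a unique, consecutive three-digit identification number", and this number identifies the subject throughout. Sections XIII.C and XVIII restrict access to the link between name and ID. They say nothing about who may know the treatment.

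Section VIII gives both arms four sessions, at Weeks 0, 4, 8 and 12. Arm 1 receives saline at three of them and BOTOX at Week 4; Arm 2 receives saline at all four. On technique it says: "Approximately 20 to 30 injections with a 20 gage needle will be given directly into the penile plaque", with the needle moved about inside the plaque. The saline is described as "10cc of preservative free normal saline for placebo and plaque breakdown injections".

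Section XII makes curvature, read by protractor from photographs, the primary outcome, and lists ultrasound measures and IIEF change as secondary. Sections V and VIII define ED as a fall in IIEF of more than 4 points. From Week 16, ED status determines whether a subject stops, continues or crosses over.

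**The concern.** The contrast is one BOTOX injection added to a needling course, against the needling course alone. It isolates the drug only if everything else is equal between arms. Needling is a physical intervention on the very structure whose curvature is measured, and its intensity is left to the operator. An injector who knows the arm could needle one arm more than the other without departing from the protocol. A reader who knows the arm could place the protractor differently. A subject who knows his arm could answer the IIEF differently.

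Section II sets out to establish efficacy, and Section VIII makes the crossover offer depend on a significant difference between arms at Week 16. Both rest on a comparison that is unprotected against these influences. Once treatment has been given and the IIEF answered, no analysis can restore that protection.

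**Working it through.** **1. Is anyone masked?**

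| Person | What the available text says |
|---|---|
| Subject | Nothing on masking |
| Injector | Nothing on masking; nothing on who prepares syringes |
| IIEF/AE collector | Nothing on masking |
| Photograph/ultrasound reader | Reader not named; nothing on masking |

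Some features are compatible with masking: equal 10 cc volumes, placebo supplied alongside BOTOX (Section III), and saline in both arms at Weeks 0, 8 and 12. None is stated to serve it.

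**2. Could the arm be known?** Section VI makes the arm a function of the number's parity. Section XVIII makes IDs consecutive. If IDs follow the order of allocation, an odd ID means Arm 1 and an even ID means Arm 2. Even if they do not, anyone who knows the enrolment order knows the arm, and learning one subject's assignment reveals all the others. Syringe coding alone would not stop this.

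**3. What can differ between arms?** A needling effect common to both arms cancels; only a difference remains. The stated range gives these extremes over four sessions:

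- low: 4 × 20 = 80 passes
- high: 4 × 30 = 120 passes
- ratio: 120/80 = 1.5

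So up to 50% more passes is possible within the range, but only if one arm is at its floor and the other at its ceiling at every session. Step 4 of the procedure covers both solutions, which suggests the same technique for both. Step 5, on the placebo arm, does not say so expressly. The protocol does not ask for passes to be counted.

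**4. Which endpoints does each route reach?**

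- Curvature (primary): unequal needling and unmasked protractor reading.
- Plaque size and blood flow: unequal needling and unmasked ultrasound reading.
- IIEF: expectation, and through it the ED classification.

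**5. What would a bias do?** The documents give no degrees-per-pass figure and no SD, and the sample size of 10 per arm has no alpha, power or effect behind it that could be reproduced. The following is therefore illustration only. Assume a two-sided 5% two-sample t-test, 10 per arm, no drug effect, and a non-drug difference between arms of b SD. The noncentrality is b/√(2/10) on 18 degrees of freedom.

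| b (assumed, SD) | Noncentrality | Chance of rejecting |
|---|---|---|
| 0 | 0 | 5.0% |
| 0.25 | 0.56 | 8.3% |
| 0.5 | 1.12 | 18.5% |
| 1.0 | 2.24 | 56.2% |

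Nothing in the documents says where in this range a real bias would fall, or that there would be one.

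**The case against.** The title pages were removed and may carry a blinding label, so the finding can speak only of the available text. That stands. A label would still not supply a procedure, nor cure allocation by parity.

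The matched volumes and saline sessions suggest that masking was intended. That may be so, but the intention then needs to be written down and made workable.

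A reader might also infer several stronger things that the documents do not support:

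- **That the injector must know the arm because he prepares the Week 4 syringe.** The product is a dried vial ("Each vial contains 100 units of vacuum-dried Clostridium botulinum type A neurotoxin components"), but no section says who reconstitutes it or where. The storage limits in Section III leave room for separate preparation.
- **That the arms will differ by 80 against 120 passes.** This is the extreme of the permitted range, not an expectation.
- **That the protocol concedes that its placebo is active.** The phrase about plaque breakdown can also be read as naming two uses of saline, Arm 2 placebo and Arm 1's saline sessions.
- **That expectation drives curvature.** Curvature is photographed in a drug-induced erection, so expectation is chiefly an IIEF problem. The ED rule acts only from Week 16, after the primary measurement.
- **That passes will go unrecorded.** The case report forms are not in the documents. What can be said is that the protocol does not require a count.
- **That a pharmacist is on hand for masked preparation.** Appendix II, item 10.4, says "notify the pharmacist, or the person responsible for the drug logs", but this is general departmental audit advice and does not establish a preparer for this trial.

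Finally, this is called a pilot. That would excuse a modest sample, but Sections II and XI still claim that it will settle whether the therapy works.

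**Conclusion.** The concern holds in this form: the available text states no masking of subject, injector, collector or reader, and the allocation and numbering rules could reveal the arm. Differential needling or unmasked reading could bias the primary endpoint; expectation could bias the IIEF and ED status. The documents show that the route is open. They do not show that bias will occur, in which direction, or how large it would be.

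The conclusion assumes that the removed front matter holds at most a label, and that Section VIII's visit-by-visit account of Arm 1 is the operative one. Reading the arm directly from the ID further assumes that IDs follow allocation order. The SD-scale illustration rests on an assumed 5% two-sided test and assumed values of b. The point should be settled before the first injection.

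**What to change.** 1. In Section V, state that the subject, injector, IIEF/AE collector and photograph/ultrasound reader are masked until that subject's Week 16 assessments are complete. Reveal the arm for crossover or continuation only then.
2. Supply identical coded 10 cc syringes at all four visits in both arms, prepared by available staff who neither inject nor assess.
3. Replace odd/even allocation in Section VI with a concealed random list that cannot be read from the subject ID.
4. State that the same needling procedure applies in both arms, and add a CRF field for passes per session so that balance can be checked.
5. Read the photographs under codes that hide both arm and visit.

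**Cost.** Amendment wording, a random list, a coding log and one CRF field; the sample size does not change. Syringe preparation must be coordinated with Section III's 30-minute limit after drawing up, and it assumes that someone other than the injector can do it.

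If the injector cannot be masked, the protocol should say so, keep the subject and reader masked, and limit the efficacy claim accordingly.

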Penile curvature secondary to scar or plaque formation along the shaft of the penis is known as Peyronie's disease. Significant penile curvatures can result in pain, poor erections, and an inability to engage in sexual intercourse. Peyronie's disease is an acquired disease of the tunica albuginea surrounding the corpora cavernosa of the penis and affects approximately 3% of the male population. The average age of onset of this disease is 57 years old. The etiology of Peyronie's disease remains unknown. However, many believe that traumatic inflammatory changes to the septal fibers of the erect penis from either blunt penile injury or repeated microtrauma associated with sexual activity.

Traditionally, treatments for Peyronie's disease have been limited and often unsuccessful. Oral medical therapies that prevent the scar formation and promote scar breakdown have been ineffective. Many patients with Peyronie's disease will require injection therapy of the penis. Injections of pharmaceutical agents directly into the Peyronie's plaque have been used for over 50 years in the treatment of clinically significant Peyronie's disease. The three most common agents used for injection therapy are verapamil, interferon, and collagenase. Intracellular calcium levels play an important role in the metabolism and synthesis of collagen. Calcium channel blockers such as verapamil increase collagenase activity and decrease collagen secretion, although quite high tissue doses are needed for this. Interferons are low molecular weight proteins involved in the normal function of the body's immune system. They are known to inhibit the proliferation of myofibroblasts, decrease collagen production, and increase the activity of collagenase. Finally, collagenase is a purified bacterial enzyme that attacks and

breaks down collagen. It has been used clinically to treat severe burns and lumbar disk disease. All three of the agents have been shown to result in mild to moderate improvement in penile curvature when compared to placebo.

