Hypertension was reported in about 2% of patients. Headaches and dizziness were reported in 2% or less of patients. About 1% of the patients complained of backache. Upper respiratory infections were reported in 4% and flu-like symptoms in 2%. Sinusitis was reported in 2% and nasal congestion and coughs in 1%. Prostatic disorders were reported in 2%. Localized pain at injection site was reported in about 2% and trauma, such as, injuries, fractures, abrasions, lacerations, and dislocations were reported in 2%.

Less than 1% of patients in clinical studies reported the following events that were judged as possibly related to the use of Caverject: testicular pain and disorder, scrotal disorder, scrotal edema, hematuria, impaired urination, urinary frequency, urinary urgency, pelvic pain, hypotension, vasodilation, peripheral vascular disorder, supraventricular extrasystoles, vasovagal reaction, hypesthesia, non-generalized weakness, diaphoresis, rash, non-application site pruritus, skin neoplasm, nausea, dry mouth, increased serum creatinine, leg cramps, and mydriasis.

LIDOCAINE®: Adverse experiences with Lidocaine are, in general, dose-related and may result form high plasma levels caused by excessive dosage, rapid absorption or inadvertent intravascular injection, or may result from a hypersensitivity, idiosyncrasy or diminished tolerance on the part of the patient.

Central nervous system symptoms that may be experienced are lightheadedness, nervenousness, apprehension, euphoria, confusion, dizziness, drowsiness, tinnitus, blurred or double vision, vomiting, sensations of heat, cold or numbness, twitching, tremors, convulsions, unconsciousness, respiratory depression and arrest.

Cardiovascular manifestations are usually depressant and are characterized by bradycardia, hypotension, and cardiovascular collapse, which may lead to cardiac arrest.

Allergic reactions are characterized by cutaneous lesions, urticaria, edema, or anaphylactoid reactions. These reactions to Lidocaine are extremely rare.

The effect of the study treatments on the ability to have erections and to have intercourse is unknown. It is not known whether the treatments the subject receives in this study will worsen or will improve his ability to have intercourse

Additional risks that may be experience by subjects participating in this study are:

The risk of developing erectile dysfunction after these injections is unknown.

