**Please circle your answer**

1. Over the past 4 weeks, how often were you able to get an erection during sexual activity?

No sexual activity .....	0
Almost never/never .....	1
A few times (much less than half of the time).....	2
Sometimes (about half of the time) .....	3
Most times (much more than half of the time).....	4
Almost always/always .....	5
  
2. Over the past 4 weeks when you had erections with sexual stimulation, how often were your erections hard enough for penetration?

No sexual activity .....	0
Almost never/never .....	1
A few times (much less than half of the time).....	2
Sometimes (about half of the time) .....	3
Most times (much more than half of the time).....	4
Almost always/always .....	5
  
3. Over the past 4 weeks when you attempted sexual intercourse, how often were you able to penetrate (enter) your partner?

Did not attempt intercourse .....	0
Almost never/never .....	1
A few times (much less than half of the time).....	2
Sometimes (about half of the time) .....	3
Most times (much more than half of the time).....	4
Almost always/always .....	5
  
4. Over the past 4 weeks during intercourse, how often were you able to maintain your erection after you had penetrated (entered) your partner?

Did not attempt intercourse .....	0
Almost never/never .....	1
A few times (much less than half of the time).....	2
Sometimes (about half of the time) .....	3
Most times (much more than half of the time).....	4
Almost always/always .....	5
  
5. Over the past four weeks, during sexual intercourse, how difficult was it to maintain your erection to completion of intercourse?

Did not attempt intercourse .....	0
Extremely difficult .....	1
Very difficult .....	2
Difficult .....	3
Slightly difficult .....	4
Not difficult .....	5
  
6. Over the past four weeks, how many times have you attempted sexual intercourse?

No attempts.....	0
One to two attempts .....	1
Three to four attempts.....	2
Five to six attempts .....	3
Seven to ten attempts .....	4
Eleven or more attempts .....	5
  
7. Over the past four weeks when you attempted sexual intercourse, how often was it satisfactory for you?

Did not attempt intercourse .....	0
Almost never/never .....	1
A few times (much less than half of the time).....	2
Sometimes (about half of the time) .....	3
Most times (much more than half of the time).....	4
Almost always/always .....	5

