## International Index of Erectile Function (IIEF) Questionnaire\*

8. Over the past four weeks, how much have you enjoyed sexual intercourse?

- No intercourse..... 0
- No enjoyment..... 1
- Not very enjoyable ..... 2
- Fairly enjoyable..... 3
- Highly enjoyable..... 4
- Very highly enjoyable ..... 5

9. Over the past four weeks, when you had sexual stimulation or intercourse, how often did you ejaculate?

- No sexual stimulation/intercourse ..... 0
- Almost never/never ..... 1
- A few times (much less than half of the time)..... 2
- Sometimes (about half of the time) ..... 3
- Most times (much more than half of the time) ..... 4
- Almost always/always ..... 5

10. Over the past four weeks when you had sexual stimulation or intercourse, how often did you have the feeling of orgasm or climax?

- No sexual stimulation/intercourse ..... 0
- Almost never/never ..... 1
- A few times (much less than half of the time)..... 2
- Sometimes (about half of the time) ..... 3
- Most times (much more than half of the time) ..... 4
- Almost always/always ..... 5

11. Over the past four weeks, how often have you felt sexual desire?

- Almost never/never ..... 1
- A few times (much less than half of the time)..... 2
- Sometimes (about half of the time) ..... 3
- Most times (much more than half of the time) ..... 4
- Almost always/always ..... 5

12. Over the past four weeks, how would you rate your level of sexual desire?

- Very low/none at all..... 1
- Low ..... 2
- Moderate ..... 3
- High..... 4
- Very high..... 5

13. Over the past four weeks, how satisfied have you been with your overall sex life?

- Very dissatisfied..... 1
- Moderately dissatisfied..... 2
- About equally satisfied and dissatisfied..... 3
- Moderately satisfied ..... 4
- Very satisfied ..... 5

14. Over the past four weeks, how satisfied have you been with your sexual relationship with your partner?

- Very dissatisfied..... 1
- Moderately dissatisfied..... 2
- About equally satisfied and dissatisfied..... 3
- Moderately satisfied ..... 4
- Very satisfied ..... 5

15. Over the past four weeks, how do you rate your confidence that you could get and keep an erection?

- Very low ..... 1
- Low ..... 2
- Moderate ..... 3
- High..... 4
- Very high..... 5

\*RC Rosen, A Riley, G Wagner et al. The international index of erectile dysfunction (IIEF): a multidimensional scale for assessment of erectile dysfunction. Urology 1997 49: 822-30.

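### The ED rule names no IIEF score, and in a man sexually inactive before Baseline, erection loss alone cannot reach its more-than-4-point threshold

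*Combined protocol and SAP*

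**What the plan says.** Section V (Design), footnote 1 to the Section VII schedule and Section VIII (Procedures) all define new ED at Week 16 as "a drop in IIEF scores of more than 4 points from Baseline IIEF score". None says which IIEF score is meant or how an answer of no activity is treated. Section XII (Data Analysis) lists change in IIEF scores as a subjective outcome, with no scoring rule, and does not list ED by arm.

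The class determines what happens next. Arm 1 men with ED have visits at Months 6, 9 and 12, while those without it finish at Week 16. Arm 2 men with ED finish at Week 16, and the others may cross over.

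Appendix I asks about the past 4 weeks, for example "Over the past 4 weeks, how often were you able to get an erection during sexual activity". The zero answers are:
- items 1-2: "No sexual activity"
- items 3-5 and 7: "Did not attempt intercourse", with equivalent zeros for items 6 and 8
- items 9-10: "No sexual stimulation/intercourse"

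Items 11-15 run from 1 to 5. Item 15 is the only one of these about erections: "how do you rate your confidence that you could get and keep an erection".

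Section IV does not require sexual activity or a minimum erectile function at entry. Section I says of the disease: "Significant penile curvatures can result in pain, poor erections, and an inability to engage in sexual intercourse". Section IX says: "The risk of developing erectile dysfunction after these injections is unknown".

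**The concern.** A rule based on a fall from Baseline works only in a man whose Baseline score has room to fall. In this questionnaire a zero on items 1-10 means that the activity did not take place, not that erectile function was poor. A man inactive before Baseline is therefore already at the floor on ten items, including five of the six about erections. If he loses his erections on study, those items cannot show it.

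The plan provides only two outcomes, ED or no ED. A man in whom the rule could not work falls into the second by default. In Arm 1 he would end at Week 16 without the continuation visits, and in Arm 2 he would stay eligible for crossover. He would also count in the denominator as a man observed not to have ED, for a harm whose frequency the protocol calls unknown. Because Section XII asks for no ED table by arm, nothing in the planned analysis would show how many such men there are.

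**Working it through.** The documents do not derive the 4-point threshold, so there is no figure of the plan's to reproduce. The check uses the score ranges in Appendix I.

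**Inputs.** Items 1-10 score 0 to 5 and items 11-15 score 1 to 5 (Appendix I). ED needs a fall of more than 4, that is, at least 5 whole points (Section V). There are 10 men per arm (Section XI). The number inactive at Baseline is not in the documents; I assume 3 of 10, range 1 to 5.

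**Step 1: largest possible fall with items 1-10 at 0 at Baseline.** The largest fall is the sum over items of highest possible Baseline score minus lowest possible Week 16 score.
- Erection items (1-5 and 15): 5 × 0 + (5 − 1) = 4. This is not more than 4, so the rule cannot be met.
- All 15 items: 10 × 0 + 5 × (5 − 1) = 20, so the rule can be met. Item 15 supplies at most 4 of the 5 points needed, so at least 5 − 4 = 1 point must come from items 11-14 (desire and satisfaction).
- Example on the total: items 13, 14 and 15 going from 3, 3, 4 to 1, 2, 1 is a fall of 10 − 4 = 6, classed as ED. With item 15 alone going from 5 to 1, the fall is 4 and he is classed as not having ED.

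**Step 2: who is not assessable on the erection items.** The lowest possible sum of items 1-5 and 15 is 0 + 1 = 1. A Baseline sum B can fall by at most B − 1, and B − 1 > 4 needs B ≥ 6. So B ≤ 5 means a qualifying fall is impossible. A fully inactive man has B equal to item 15, which is 1 to 5, so all such men are captured.

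**Step 3: what zero cases would show.** With 0 events in n informative men, the one-sided 95% upper bound is 1 − 0.05^(1/n).

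| Inactive of 10 (assumed) | n | Upper bound |
|---|---|---|
| 0 | 10 | 25.9% |
| 1 | 9 | 28.3% |
| 3 | 7 | 34.8% |
| 5 | 5 | 45.1% |

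**Step 4: largest understatement of the rate.** Assume a true ED risk of 30%, equal in active and inactive men, with every affected inactive man missed. The apparent rate is then 0.30 × 7/10 = 21% for 3 of 10 inactive (0.30 × 9/10 = 27% for 1; 0.30 × 5/10 = 15% for 5).

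**Step 5: the opposite error.** A man active at Baseline with no activity before Week 16 can fall by up to 5 × 5 = 25 points on items 1-5, and 10 × 5 = 50 on items 1-10, with no loss of erections.

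**The case against.** The strongest reply is that the plain reading of the rule is the 15-item total, because the whole form is in Appendix I and no subscore is defined. On that reading an inactive man can be classed as ED: of the 5^5 = 3125 possible Baseline patterns on items 11-15, 2999 leave room for a fall of more than 4. This stands, so a reader who infers that such a man can never be classed as ED goes further than the documents allow. But room to fall is not detection. The count does not change the fact that a desire or satisfaction item must fall as well, so the class does not measure erection loss in him.

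Four further points stand in part.
- Section I speaks of inability to have intercourse, which by itself zeroes items 3-8 only. The full floor needs no sexual activity or stimulation at all, a narrower group, and the documents do not show that it is common.
- Adverse events are collected at every clinic and telephone contact from Week 0 (Section VII) and followed to resolution (Section XIII.D), so ED may come to light that way. Nothing says that such a report changes the ED class.
- It is tempting to say that a missed Arm 2 man goes on to BOTOX. Section VIII makes crossover optional and conditional on a significant benefit, while Section V states it without that condition. The two need reconciling; all that follows here is that he stays eligible.
- It is also tempting to say that the ED rate is under-stated overall. Step 5 shows an error in the other direction, so the net direction is unknown.

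**Conclusion.** The point holds in this form: the score behind the ED rule is not named, and for a man fully inactive before Baseline, erection loss alone cannot meet the rule under either reading. On the erection items he can never meet it; on the total he needs a fall in items 11-14 as well. The two-way class then records as absence of ED something the rule could not detect.

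The size depends on the number of inactive men, for which the documents give no data. If there are none, the classification is unaffected. With 1 to 5 of 10 per arm, and the erection items as the score, zero cases would support an upper bound of 28.3% to 45.1% instead of 25.9%. On the total, inactive men carry some information, so the loss is smaller. With 3 of 10 inactive, an apparent 21% for a true 30% is the worst case, not an expected value: it requires every affected inactive man to be missed and no false ED among the rest.

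**What to change.** - **Sections V, VII (footnotes) and VIII:** name one score for the ED rule, preferably the sum of items 1-5 and 15, which is already collected. Use the same score to define a third class, ED not assessable: Baseline sum of 5 or less. Using one score for both prevents a man from being classed as ED on the total and as not assessable on the erection items.
- **Section XII:** report ED by arm with an exact 95% confidence interval among assessable men, and give the not-assessable count beside it. Show separately the men whose Week 16 fall comes from no-activity zeros, so that the opposite error is also visible.
- **Week 16 pathway:** the score and the third class bear on who continues, ends or may cross over. The sponsor must state which pathway applies to not-assessable men and reconcile Sections V and VIII. I propose no clinical rule.

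The cost is one derived variable and one table from data already collected, and a somewhat wider interval for ED. The third class will also contain some active men whose erections were already very poor at Baseline; that is appropriate, because the rule cannot register a qualifying fall in them either.
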